2. OBJECTIVES

The primary objective of this diagnostic study is to determine the diagnostic accuracy of dry electrode cap EEG for diagnosis of LVO-a, when performed by paramedics in the ambulance in patients with a suspected AIS.

The secondary objectives of this study are:

- Determining the diagnostic accuracy for LVO-a detection of several existing EEG data based algorithms (e.g. Weighted Phase Lag Index, delta/alpha ratio);
- Assessing the logistical and technical feasibility of paramedics performing dry electrode cap EEG in the ambulance in suspected AIS patients;
- Developing one or more novel EEG data based algorithms with an optimal diagnostic accuracy for LVO-a detection in suspected AIS patients with ambulant dry electrode cap EEG.

3. STUDY DESIGN

The ELECTRA-STROKE is an investigator-initiated, diagnostic study, that consists of four phases (see below).

STUDY PHASE 1: OPTIMIZING MEASUREMENT TIME, SOFTWARE SETTINGS AND DATA TRANSFER LOGISTICS IN PATIENTS IN WHOM A REGULAR EEG HAS BEEN/WILL BE PERFORMED FOR STANDARD MEDICAL CARE IN A NON-EMERGENCY SETTING

This phase will be carried out in the outpatient clinic of the department of Clinical Neurophysiology of a single center (Amsterdam UMC, location AMC). We will perform dry electrode cap EEGs on patients in whom a regular EEG has been/will be performed for standard medical care. We will compare the regular EEG to the dry electrode cap EEG and this way try to optimize the dry electrode cap EEG measurement, software settings, data transfer logistics and measurement time in a population of patients less vulnerable than our target population, in a non-emergency setting.

STUDY PHASE 2: OPTIMIZING MEASUREMENT TIME, SOFTWARE SETTINGS AND DATA TRANSFER LOGISTICS IN PATIENTS CLOSE TO TARGET POPULATION IN A NON-EMERGENCY SETTING.

This phase will be carried out in the brain care unit of a single center (Amsterdam UMC, location AMC). We will perform dry electrode cap EEGs in a population close to our target population – patients that have been admitted with an AIS and an LVO-a – in a non-emergency setting. We will test technical feasibility of the dry electrode cap EEG in patients that are, in part, unable to cooperate with the procedure (e.g. patients that because of lowered consciousness or agitation will not keep their head still).

STUDY PHASE 3: VALIDATION OF EXISTING ALGORITHMS AND DEVELOPMENT OF NEW ALGORITHM(S) IN PATIENTS IN THE EMERGENCY ROOM

This phase will be carried out in the ER of a single center (Amsterdam University Medical Centers, location AMC). In this phase, we will perform dry electrode cap EEGs in patients that are presented to the ER of the coordinating hospital with a clinically suspected AIS, according to the paramedic that presents the patient, or with a known LVO-a. The last category of patients have undergone an initial work-up in a primary stroke center, where the diagnosis LVO-a has been made, and are transferred to our hospital to undergo EVT. The EEG data of this 'enriched' population, with a higher incidence of LVO-a compared to the primary target population, will be used to validate several existing algorithms and to develop one or more new algorithms for diagnosis of LVO-a.

STUDY PHASE 4: VALIDATION OF ALGORITHMS IN THE AMBULANCE

This phase is the only multi-center phase of this study. It will be carried out in the ambulances of one ambulance station in Amsterdam and one ambulance station in Alkmaar. These ambulances bring patients with a suspected acute stroke to the following hospitals: AMC, VUMC and OLVG West and Noordwest Ziekenhuisgroep, location Alkmaar. These will therefore be the centers participating in this study phase, as well as the Ambulance Amsterdam. The EEG data will be used to validate several existing algorithms (among which is the Brain Symmetry Index) and the algorithm(s) developed in phase 3. Technical and logistical feasibility of performing ambulant EEGs in patients with a suspected AIS in the ambulance will also be assessed.

Phase 4 will start with a 'run in' phase. The objective of this phase is to assess technical and logistical feasibility of performing ambulant EEGs in patients with a suspected AIS, before commencing inclusion of the prespecified study population. Inclusion will not be consecutive at this stage.

The four phases will not necessarily run consecutively; they may also, in part, run simultaneously. Each phase consists of performing a single dry electrode cap EEG per patient and collecting information on patient characteristics, medical history, medication use, physical and neurological examination performed by the treating physician, imaging studies, diagnosis and treatment as well as logistical and technical information, obtained from the patient, the Emergency Medical Service (EMS) and the treating physician. There are no follow up visits. The study will run until the number of patients required according to the sample size calculation have been included for each phase.

4. STUDY POPULATION

4.1 POPULATION (BASE)

STUDY PHASE 1

We will recruit patients in whom a regular EEG has been/will be performed for standard medical care in the outpatient clinic of the Clinical Neurophysiology department of the AMC, who meet the criteria described in chapter 4.2 and 4.3.

STUDY PHASE 2

We will recruit patients with a that have been admitted to the hospital with an LVO-a, who meet the criteria described in chapter 4.2 and 4.3.

STUDY PHASE 3

We will recruit patients with a suspected AIS or a known LVO-a in the ER, who meet the criteria described in chapter 4.2 and 4.3.

STUDY PHASE 4

We will recruit patients with a suspected AIS in the ambulance, who meet the criteria described in chapter 4.2 and 4.3.

4.2 INCLUSION CRITERIA

STUDY PHASE 1

- Age of 18 years or older;
- Patient is in the outpatient clinic of the Clinical Neurophysiology department of the AMC, because a regular EEG has been/will be performed on him/her for standard medical care;
- Written informed consent by patient.

STUDY PHASE 2

- A diagnosis of acute ischemic stroke caused by a large vessel occlusion in the anterior circulation (intracranial carotid artery or proximal (M1/M2) middle cerebral artery confirmed by neuro-imaging (CTA or MRA);
- Stroke onset <72 hours before expected time of performing EEG;
- Age of 18 years or older;
- Written informed consent by patient or legal representative.

STUDY PHASE 3

- Suspected acute ischemic stroke, as judged by the paramedic presenting the patient to the ER or known AIS with an LVO-a;
- Onset of symptoms or, if onset was not witnessed, last seen well <24 hours ago;

- Age of 18 years or older;
- Written informed consent by patient or legal representative (deferred).

STUDY PHASE 4

- Suspected acute ischemic stroke as judged by the attending paramedic;
- Onset of symptoms or, if onset not witnessed, last seen well <24 hours ago;
- Age of 18 years or older;
- Written informed consent by patient or legal representative (deferred).

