Phase 1: Optimization of measurement time and software settings of the dry electrode cap EEG in a non-emergency setting in patients in whom a regular EEG is/will be performed for standard medical care.

Phase 2: Optimization of measurement time and software settings of the dry electrode cap EEG in patients close to our target population in a non-emergency setting.

Phase 3: Validation of several existing algorithms and development of one or more new algorithms for LVO-a detection, as well as optimization of logistics and software settings of the dry electrode EEG cap in patients close to our target population in an in-hospital emergency setting.

Phase 4: Validation of several existing algorithms and algorithms developed in phase 3 for LVO-a detection in patients with a suspected AIS in the ambulance, as well as assessment of technical and logistical feasibility of performing EEG with dry electrode caps in patients with a suspected AIS in the ambulance.

STUDY POPULATION

Phase 1: Patients in the outpatient clinic of the Clinical Neurophysiology department of the AMC, in whom a regular EEG has been/will be performed for standard medical care.

Phase 2: Patients with an AIS admitted to the Neurology ward of the coordinating hospital with an LVO-a (after reperfusion therapy).

Phase 3: Patients with a suspected AIS in the emergency room (ER) of the coordinating hospital (before reperfusion therapy).

Phase 4: Patients with a suspected AIS in the ambulance.

INTERVENTION

Performing a dry electrode cap EEG (in phase 1 in the outpatient clinic, in phase 2 during hospital admission, in phase 3 in the ER and in phase 4 in the ambulance).

MAIN END POINTS

- Primary end point: the area under the receiver operating characteristics (ROC) curve of the theta/alpha ratio for diagnosis of LVO-a, based on dry electrode EEG performed by paramedics in the ambulance in suspected AIS patients;
- Secondary end points:

- Sensitivity, specificity, positive predictive value (PPV) and negative predictive value (NPV) of the theta/alpha ratio, and test characteristics of other existing EEG data based algorithms for LVO-a detection (e.g. Weighted Phase Lag Index, delta/alpha ratio);
- Logistical and technical feasibility of paramedics performing dry electrode cap EEG in the ambulance in suspected AIS patients ;

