4.3 EXCLUSION CRITERIA

STUDY PHASE 1

- Injury or active infection of electrode cap placement area.

STUDY PHASE 2

- Injury or active infection of electrode cap placement area.

STUDY PHASE 3

- Injury or active infection of electrode cap placement area.

STUDY PHASE 4

- Injury or active infection of electrode cap placement area.

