Informed consent is fundamental for patient participation in any type of research. However, in acute stroke research, the 'time is brain' principle conflicts with this. For study procedures that need to be performed in the acute setting, asking informed consent in a way that the patient or legal representative has the time to calmly consider the information and ask questions means losing valuable time: an hour delay in initiation of reperfusion therapy (IVT or EVT) in AIS causes a 5-8% decrease in chance of functional independence 3 months after the stroke^{8,9}. Also, asking for informed consent in the acute setting is unlikely to result in a decision that is well thought through, because the patient or legal representative may be overwhelmed and under psychological stress³⁶. Finally, many patients with an AIS are unable to comprehend information regarding study participation due to lowered consciousness, aphasia or anosognosia (not realizing the severity of one's own disease, often due to a lesion of the non-dominant cerebral hemisphere). Only including patients that are capable of giving informed consent would mean selecting a sub group of patients with relatively mild neurological symptoms that is not representative of the population of patients with an LVO-a. A legal representative is often not present in the acute phase³⁷. For the above mentioned reasons, several acute stroke trials have been conducted where informed consent was not required prior to randomization³⁸. According to the Medical Research Human Subjects Act (in Dutch: WMO), for research that can only be conducted in an emergency setting it is allowed to perform study procedures without prior informed consent, if inclusion in the study may benefit the person in urgent need of medical treatment, for as long as the circumstances preventing the giving of consent exist.

Performing an EEG in patients with a suspected AIS in the short time window prior to initiation of treatment is necessary in this study, because the objective is to study the diagnostic accuracy of the ambulant EEG for LVO-a. As soon as the occlusion is being treated (by IVT and/or IAT), this is no longer possible. Although participation in this study does not benefit the patient, it is very important that a

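### Phase 3 is described as pre-reperfusion, but its criteria admit transferred LVO-a patients who may already have had thrombolysis, and section 10 has no rule for their EEGs

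*Combined protocol and SAP*

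**What the plan says.** Two places tie the phase 3 EEG to the time before treatment. The Summary (study population) describes phase 3 as "Patients with a suspected AIS in the emergency room (ER) of the coordinating hospital (before reperfusion therapy"), in contrast with phase 2, which is placed after it. Section 11.2, in its discussion of deferred consent, argues that the recording has to be made in the short window before treatment because the aim is to study accuracy for LVO-a: "As soon as the occlusion is being treated (by IVT and/or IAT), this is no longer possible".

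The operative sections carry no such condition.

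- Section 4.2 admits "Suspected acute ischemic stroke, as judged by the paramedic presenting the patient to the ER or known AIS with an LVO-a", with the time limit "Onset of symptoms or, if onset was not witnessed, last seen well <24 hours ago", an age limit and deferred consent.
- The only phase 3 exclusion in section 4.3 is "Injury or active infection of electrode cap placement area".
- Section 3 explains who the known-LVO-a patients are: "The last category of patients have undergone an initial work-up in a primary stroke center, where the diagnosis LVO-a has been made", and they "are transferred to our hospital to undergo EVT".
- Section 5 and the table in section 8.3 place the phase 3 EEG at arrival in the coordinating hospital's ER.
- The notes to that table collect the start times of IVT and EVT and the transfer times.
- Section 10 compares the EEG result with LVO-a status as diagnosed by the treating physician. It does not use the treatment times.

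**The concern.** A patient who received IVT at the primary stroke center and then arrives for EVT meets section 4.2 but falls outside the population in the Summary. By section 11.2's own reasoning, that patient's EEG no longer answers the question. Section 1 calls IVT standard treatment for acute ischemic stroke, so such patients are plausible. The coordinating hospital records the EEG on arrival, which should put it before EVT there. It does not put it before IVT given elsewhere.

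The difficulty is where these EEGs would sit. Known-LVO-a transfers are cases by definition, whereas patients without an LVO-a come almost entirely from direct presentations recorded on first arrival. Prior IVT, possible recanalisation and the extra delay of transfer would therefore be found almost only among cases. An estimate of sensitivity or AUC, or a fitted model, could then partly reflect treatment or delay instead of occlusion. The algorithms are meant for untreated patients in the ambulance.

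**Working it through.** **Comparing the sections.** Taking an LVO-a patient given IVT before transfer and recorded on arrival:

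| Section | Is this EEG admissible? |
|---|---|
| Summary, phase 3 | No, reperfusion therapy has begun |
| 11.2 | No, accuracy can no longer be studied |
| 3 | Yes, transfers with a known LVO-a are included |
| 4.2 and 4.3 | Yes, no criterion concerns treatment |
| 10 | Analysed like any other, no rule |

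Section 11.2 speaks of the ambulant EEG, but section 12.1 uses that term for phases 3 and 4, and the caption of Figure 1 covers both, so the statement applies to phase 3.

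**The plan's own figure.** Section 4.4 plans 60 LVO-a cases at an incidence of about 20%: 60 / 0.20 = 300. This reproduces.

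**Transfers among the 60 cases.** The documents give no count. Two approaches bracket it.

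- Section 1 says about half of EVT-eligible patients are first admitted elsewhere. Applied here, 0.5 × 60 = 30.
- Suppose every transfer has an LVO-a and direct presenters have incidence p. Then t + p(300 − t) = 60, so t = (60 − 300p) / (1 − p). With the ambulance figures in section 4.4, p = 0.07 gives 39 / 0.93 = 41.9, and p = 0.05 gives 45 / 0.95 = 47.4.

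The range is therefore about 30 to 47.

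**EEGs after IVT.** The share of transfers given IVT first is not in the documents. I assume 30% to 70%.

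- Low: 30 × 0.30 = 9, or 9/60 = 15% of cases.
- High: 47.4 × 0.70 = 33.2, about 33, or 33/60 = 55% of cases.

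**Cases left if these are set aside.** 60 − 9 = 51, down to 60 − 33 = 27. The 95% half-width at an assumed sensitivity of 80% is 1.96 × √(0.80 × 0.20 / n):

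| LVO-a cases | Half-width (points) |
|---|---|
| 60 | 10.1 |
| 51 | 11.0 |
| 40 | 12.4 |
| 27 | 15.1 |

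I do not convert the 9 to 33 EEGs into a change in sensitivity. That would need a reopening rate and an effect of partial reperfusion, neither of which is in the documents, and the direction of confounding by treatment and delay cannot be predicted.

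**The case against.** The strongest reply is that the damage is contained. The primary end point (section 8.1.1) is the AUC of the theta/alpha ratio in the ambulance, which phase 3 enrolment does not touch. Section 10 has phase 4 determine its own cut-offs, and algorithm development uses data from both phases. Phase 4 then tests the phase 3 algorithms in the target population. Enrichment with transfers is an openly stated choice. All of this stands, and a reader who inferred that the trial's main result or its ambulance cut-offs are compromised would be going beyond the documents. What remains is the phase 3 accuracy results and the phase 3 share of the development data. That share is not small: on planned numbers phase 3 supplies 60 LVO-a cases, against about 174 × 0.05 = 8.7 in the evaluable phase 4 sample.

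A reader might also infer that transferred cases are labelled positive from the referring hospital's scan. The documents do not say so. Section 10 uses the treating physician's diagnosis, and the table in section 8.3 collects the final diagnosis at discharge, when later vessel findings could be taken into account.

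Nor do the documents state that any transferred patient received IVT; that is inferred from IVT being standard treatment and from the work-up at the primary center. The size is therefore a range built on assumptions. The contradiction between sections does not depend on it.

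Finally, phase 3 is single-center and the investigators screen patients themselves, so they may in practice apply the Summary's restriction. If they do, the criteria should say so.

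**Conclusion.** The inconsistency is real and can be read directly from the text: the Summary and section 11.2 restrict phase 3 to EEGs before treatment, sections 3, 4.2 and 4.3 do not, and section 10 is silent although the necessary times are collected. Followed as written, the plan would place post-IVT EEGs almost wholly among LVO-a cases and confound treatment with the target condition in the phase 3 accuracy estimates and in the phase 3 part of the development data.

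Confidence is high in the contradiction and low in its size. About 9 to 33 of the 60 LVO-a EEGs would be affected, assuming 30 to 47 transfers and prior IVT in 30% to 70% of them. The phase 4 primary end point and the cut-offs derived in phase 4 are outside the concern. It should be corrected, but it does not call the main result into question.

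**What to change.** 1. Reconcile the Summary and sections 3, 4.2 and 11.2, so that they agree on whether patients already given IVT belong in phase 3. The choice is the sponsor's.
2. State in section 10 that the main phase 3 accuracy and development set consists of EEGs started before any IVT or EVT, using the treatment start times listed under section 8.3 and the EEG time stored under section 12.1.
3. Report all phase 3 patients as a secondary analysis, split by prior IVT.
4. Confirm that the recorded IVT start includes treatment at the referring hospital, since the section 8.3 table lists phase 3 treatment at arrival in the ER. State how a missing start time is handled.

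The change is a few sentences and needs no new procedure, but it has a price. The main set holds fewer LVO-a cases, with the wider intervals shown above. Transfers who did not receive IVT are a selected group, and this should be said when results are reported. Nor does the restriction remove the difference in onset-to-EEG delay between transfers and direct presenters. The all-patient analysis keeps every recording in the report.

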4.3 EXCLUSION CRITERIA

STUDY PHASE 1

- Injury or active infection of electrode cap placement area.

STUDY PHASE 2

- Injury or active infection of electrode cap placement area.

STUDY PHASE 3

- Injury or active infection of electrode cap placement area.

STUDY PHASE 4

- Injury or active infection of electrode cap placement area.

4.4 SAMPLE SIZE CALCULATION

STUDY PHASE 1

For study phase 1, where we aim to optimize measurement time, software settings and data transfer logistics in patients in the outpatient clinic of the Clinical Neurophysiology department of the AMC, we

plan to include 20 patients or less, depending on the judgement of the investigators of when the optimal settings and logistics have been found.

STUDY PHASE 2

For study phase 2, where we aim to optimize measurement time, software settings and data transfer logistics in a population of patients with an AIS in a non-emergency setting, we plan to include 20 patients or less, depending on the judgement of the investigators of when the optimal settings and logistics have been found.

STUDY PHASE 3

For study phase 3, where we aim to validate existing algorithms and to develop one or more new algorithms, we plan to include 60 patients with an LVO-a. Because the coordinating center, where this phase will be conducted, is the only hospital in its region performing EVT, many patients with an LVO-a are transported here. In the population of suspected ischemic stroke patients in this hospital's ER, including patients transferred for EVT, the incidence of LVO-a is approximately 20% based on data from our own stroke database. Therefore, we aim to include 300 patients in this phase (approximately 60 patients with an LVO-a and 240 patients without an LVO-a) or less, depending on the judgement of the investigators of when the goal of this study phase is achieved.

STUDY PHASE 4

For study phase 4, where we aim to validate existing algorithms and one or more new algorithms for LVO-a detection, our primary outcome measure is the specificity of the dry electrode cap EEG in a population of patients with a suspected AIS. Sample size calculation is based on an expected specificity of 70% for LVO-a. Originally, sample size calculation was based on an expected LVO-a rate of 7% and a dropout rate of 20%. However, an interim analysis, based on 137 suspected stroke patients in whom an EEG was performed in the ambulance, showed an actual incidence of LVO-a of 5% and a dropout rate of 58%. Patients considered as a 'drop out' had insufficient EEG data quality (n=72), onset of symptoms >24 hours before EEG registration (n=4) or did not give consent for participation in the study (n=3). The EEG data quality increased over the course of the study, so we expect a lower dropout rate for future EEG registrations. Based on these interim data, we adjusted the sample size for phase 4 of the study as follows.

With an incidence of LVO-a of 5% among patients with a clinically suspected AIS in the ambulance, an alpha of 0.05, and a maximum margin of error of 7%, 174 patients with a suspected AIS are required²¹. Assuming a dropout rate of 55%, we intend to recruit 386 patients with a suspected AIS. A patient is considered a 'drop out' if no informed consent is/can be obtained, if no information on the diagnosis made by the treating physician is/can be obtained, or if the EEG measurement is of insufficient technical quality, as judged by the clinical neurophysiologist. Patients included in the 'run in' phase are excluded from the primary analysis and thus not included in our sample size calculation. In the 'run in' phase, we will additionally include 50 patients or less.

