8. METHODS

8.1 STUDY PARAMETERS/END POINTS

8.1.1 MAIN STUDY PARAMETER/END POINT

The primary end point of the study is the area under the ROC curve of the theta/alpha ratio for diagnosis of LVO-a, based on dry electrode EEG performed by paramedics in the ambulance in suspected AIS patients.

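### Phase 4 accuracy will be estimated only in patients whose ambulance EEG was readable; about half of those tested were not at interim, and no analysis includes them

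*Combined protocol and SAP*

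**What the plan says.** Section 2 gives this as its main objective: "diagnostic accuracy of dry electrode cap EEG for diagnosis of LVO-a, when performed by paramedics in the ambulance in patients with a suspected AIS". In Section 8.1.1 the primary end point is the AUC of the theta/alpha ratio, "based on dry electrode EEG performed by paramedics in the ambulance in suspected AIS patients". Neither is limited to recordings that can be read.

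Section 4.4 lists the reasons for counting a phase 4 patient as a drop-out. They are missing consent, a missing diagnosis, "or if the EEG measurement is of insufficient technical quality, as judged by the clinical neurophysiologist". Of 137 patients with an ambulance EEG at the interim look, 58% were drop-outs: they "had insufficient EEG data quality (n=72), onset of symptoms >24 hours before EEG registration (n=4"), or they refused consent (n=3). The response was to enlarge recruitment: "Assuming a dropout rate of 55%, we intend to recruit 386 patients with a suspected AIS". Section 4.4 also notes: "The EEG data quality increased over the course of the study, so we expect a lower dropout rate for future EEG registrations". On the run-in it says: "Patients included in the 'run in' phase are excluded from the primary analysis and thus not included in our sample size calculation"; for that stage the number is given as follows: "we will additionally include 50 patients or less". It does not say whether the 137 include run-in patients.

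For phase 4, Section 10 plans ROC curves, an optimal cut-off, and sensitivity, specificity, NPV and PPV with 95% confidence intervals. It defines no analysis set, gives no rule for an unreadable EEG and plans no supplementary analysis. Technical feasibility is a secondary end point (Section 8.1.2) without a defined analysis. Section 8.5 commits to reporting reasons for withdrawal.

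**The concern.** A patient lost for lack of consent or diagnosis contributes no information. A patient whose EEG was recorded but could not be read is different: the test was applied and failed. Removing these patients as drop-outs leaves an estimate of how well the EEG works when it works. Recruiting more patients restores precision for that estimate but does not widen the group it describes.

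The EEG does not steer hospital choice in this study. The triage use proposed in Section 1, however, would meet unreadable recordings, and those patients would still have to be taken somewhere. Section 1 says that a false negative delays treatment and that specificity matters even more. Counting unreadable recordings as negative or as positive moves these two measures in opposite directions.

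An overall failure rate does not fill the gap, because all-patient sensitivity depends on the failure rate among LVO-a patients. The plan does not commit to reporting that. There is reason to look: the phase 2 description in Section 3 mentions patients who cannot keep still because of lowered consciousness or agitation, and Section 11 warns that including only patients able to consent would leave a milder, unrepresentative group. That is a reason to check for a relation, not evidence of one.

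**Working it through.** **The plan's own figures (Section 4.4).** Inputs: specificity 70%, margin 7%, alpha 0.05 (taken as two-sided), LVO-a 5%, loss 55%.

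- Non-LVO-a patients: 1.96² × 0.70 × 0.30 / 0.07² = 164.6.
- All evaluable patients: 164.6 / 0.95 = 173.3, rounded up to 174, as stated.
- Recruited: 174 / 0.45 = 386.7; the plan states 386.
- Interim drop-outs: 72 + 4 + 3 = 79; 79/137 = 57.7%, stated as 58%.

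The sample size arithmetic is sound, and it confirms that the accuracy analysis is sized on about 45% of those recruited.

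**Unreadable share at interim.** 72/137 = 52.6% (95% Wilson interval 44% to 61%). Of all drop-outs, 72/79 = 91%.

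**Effect of the run-in.** Assume that 50 of the 137 were run-in patients and that run-in recordings were no more readable than later ones. If all 50 were unreadable, the later share is (72 − 50)/(137 − 50) = 22/87 = 25%. If readability did not differ, it is 53%. This range covers the later recordings within the 137. It is not a floor for recordings still to come.

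**What the planned loss implies.** If the interim mix of reasons holds (assumption), the unreadable share is 0.55 × 72/79 = 50.1%, or 386 × 0.501 ≈ 193 patients. If the 5% LVO-a rate applies equally to readable and unreadable (assumption):

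- unreadable LVO-a patients: 193 × 0.05 ≈ 10;
- analysed LVO-a patients: 174 × 0.05 ≈ 9.

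**Effect on accuracy in all tested patients.** Let u be the unreadable share, unrelated to LVO-a, and Se and Sp the values in readable EEGs.

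- Unreadable as negative: sensitivity Se(1 − u), specificity Sp(1 − u) + u.
- Unreadable as positive: sensitivity Se(1 − u) + u, specificity Sp(1 − u).
- Under either rule, sensitivity + specificity − 1 = (Se + Sp − 1)(1 − u).

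Take Sp = 70% (Section 4.4) and Se = 70% (assumption; the documents give none):

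| u | Unreadable as negative, Se/Sp | Unreadable as positive, Se/Sp | Se + Sp − 1 |
|---|---|---|---|
| 0% | 70% / 70% | 70% / 70% | 0.40 |
| 20% | 56% / 76% | 76% / 56% | 0.32 |
| 25% | 52.5% / 77.5% | 77.5% / 52.5% | 0.30 |
| 50% | 35% / 85% | 85% / 35% | 0.20 |

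**Why the split by LVO-a status matters.** Hold the overall unreadable share at 50%, count unreadable as negative, and vary the share among LVO-a patients (assumption):

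- 30% of LVO-a unreadable: non-LVO-a share (0.50 − 0.05 × 0.30)/0.95 = 51.1%; sensitivity 0.70 × 0.70 = 49%; specificity 0.70 × 0.489 + 0.511 = 85%.
- 70% of LVO-a unreadable: non-LVO-a share (0.50 − 0.05 × 0.70)/0.95 = 48.9%; sensitivity 0.70 × 0.30 = 21%; specificity 0.70 × 0.511 + 0.489 = 85%.

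The same overall failure rate is compatible with sensitivity from 21% to 49%, while specificity hardly moves.

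**The case against.** The strongest reply is that the restriction is open and the two questions are handled separately. Section 4.4 states the drop-out rule, the 72 of 137 and the 55% planning rate. Technical feasibility has its own end point and a run-in devoted to it. An unreadable EEG yields no prediction, so leaving it out of a predicted-versus-diagnosed comparison is a defensible design. This stands to the extent that the readable-EEG AUC can remain primary. It does not close the gap, because the feasibility end point has no defined analysis and nothing commits to a split by LVO-a status. The documents do not rule such a split out; it is simply not prespecified.

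A second reply is that quality was improving, so the future share could fall below 25%. That is possible, and the future share is uncertain. The plan nevertheless lowered its assumed loss only from 58% to 55%, and at 20% unreadable the shift in sensitivity is still 14 percentage points under counting as negative.

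Third, the illustration forces a missing result into positive or negative, whereas an unreadable EEG might simply leave existing routing in place. That is fair. The three-way table keeps unreadable as its own category, and the two counting rules mark the extremes.

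Fourth, the split will be imprecise. With about 19 LVO-a patients, 10 of them unreadable, the 95% Wilson interval for 10/19 is 32% to 73%. This also stands. It limits what the table can settle and is a reason to report the interval.

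**Conclusion.** The concern holds. Following the drop-out rule as written removes about half of the tested patients from every accuracy measure, and Section 10 offers nothing that brings them back. The results will therefore answer the objective for readable EEGs only. The planned AUC remains valid for that group, and no bias in it has been shown.

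The firm figure is 72/137 = 52.6% unreadable at interim. The projection of about 193 of 386 rests on the interim mix of drop-out reasons continuing. The accuracy shifts rest on an assumed 70% sensitivity and, in the main table, on readability being unrelated to LVO-a. At the unreadable shares shown for the later interim recordings and implied by the planned loss (25% and 50%), the change in specificity is 7.5 to 15 percentage points when unreadable counts as negative and 17.5 to 35 when it counts as positive. All of these exceed the 7% margin on which the sample size rests. The plan should be changed, but the primary analysis need not be.

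**What to change.** Keep the readable-EEG AUC as primary and state in Sections 8.1.1 and 10 that it applies to readable EEGs. Add to Section 10 a supplementary analysis of all eligible phase 4 patients outside the run-in whose data may be used and whose diagnosis is known:

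1. For the theta/alpha ratio, hold the cut-off from the readable-EEG analysis fixed, without re-optimising it, and cross-tabulate EEG positive, negative and unreadable by LVO-a status.
2. Report sensitivity and specificity with 95% confidence intervals, counting unreadable as negative and, separately, as positive. Give the unreadable share by LVO-a status with its interval.
3. State how many patients with an unreadable EEG could not be included because the diagnosis or permission to use the data was missing.
4. State whether the 137 interim patients include run-in patients.

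The cost is one table and the measures derived from it. It uses the EEG quality verdict and the diagnosis that Section 11.2 says is registered before consent. Sample size and primary end point do not change. The documents do not confirm that diagnosis and consent were completed for the 72, so some collection may be needed and some patients may stay out. The sponsor should also expect less favourable or less certain all-patient figures: counting unreadable as negative lowers sensitivity and raises specificity, and counting it as positive does the reverse.
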